4.1 Inclusion Criteria

All subjects accepted for this trial must:

- Be scheduled for sub-lobar radioembolization therapy of a previously untreated HCC mass < 6 cm visible on grayscale ultrasound.
- Be at least 18 years of age.
- Be medically stable.
- If a female of child-bearing age, have a negative pregnancy test prior to each ultrasound exam.
- Have signed Informed Consent to participate in the study.

4.2 Exclusion Criteria

Subjects with any of the following conditions or who have had the following procedures will be excluded from this trial:

- Females who are pregnant or nursing.
- Patients who are medically unstable, patients who are seriously or terminally ill, and patients whose clinical course is unpredictable. For example:
 - Patients on life support or in a critical care unit.
 - Patients with unstable occlusive disease (eg, crescendo angina)
 - Patients with clinically unstable cardiac arrhythmias, such as recurrent ventricular tachycardia.
 - Patients with uncontrolled congestive heart failure (NYHA Class IV)
- Patients with recent cerebral hemorrhage.
- Patients with known sensitivities to albumin, blood, or blood products
- Patients with known hypersensitivity to perflutren
- Patients with known cardiac shunts.
- Patients with known congenital heart defects.
- Patients with severe emphysema, pulmonary vasculitis, or a history of pulmonary emboli.
- Patients with respiratory distress syndrome.
- Patients with a history of bleeding disorders
- Patients with bilirubin levels > 2 mg/dL

Subject identification will be maintained with a study specific alphanumeric code including the subject number (01-104).

5. MEDICATIONS

Optison will be purchased from GE Healthcare, Princeton, NJ.

Optison is a sterile non-pyrogenic suspension of encapsulated perflutren microbubbles [Goldberg et al 2001; Miller & Nanda 2004]. The contrast agent consists of a human serum albumin shell with perflutren core and contains 5.0 - 8.0 x 10⁸ microspheres/ ml. The microbubble agent is supplied in a standard-size 3 ml vial and is prepared by manually shaking the vial. Detailed instructions are provided in the Optison Product Insert, found in Appendix B.

Optison will be stored in a secure refrigerator, with only the study investigators and research personnel having access. Unused drug and empty vials will be properly disposed of after reconciling the log of study drug kept at Thomas Jefferson University. Study drug will be transported from the secure refrigerator to the patient bedside by the research coordinator or principal investigators.

5.1 Administration

Contrast agent will be prepared and administered by the research nurse or a physician co-investigator. All contrast injections will be supervised by a board certified physician. Resuscitation equipment and trained personnel will be immediate proximity to the patient during each contrast-enhanced ultrasound exam. Optison will be administered by IV infusion through an angiocatheter placed in a peripheral arm vein, preferably an antecubital vein. Five milliliters of Optison will be activated by hand mixing for 30 seconds and suspended in a 50 ml bag of saline. The saline/UCA mixture will then be infused through the IV at a rate of 120 ml/hour. Subjects will be instructed not to move their arm during the administration of the contrast agent.

5.2 Contraindications

Optison should not be administered to patients with known or suspected hypersensitivity to perflutren, blood, or blood products. The safety of Optison in patients with 1) right-to-left, bi-directional or transient right-to-left cardiac shunts; 2) severe emphysema, pulmonary vasculitis or a history of pulmonary emboli; 3) respiratory distress syndrome has not been studied. Therefore, patients with any of these conditions will be excluded from participation.

5.3 Randomization

Patients will be randomly assigned to either the experimental (UTMD + radioembolization) or control group (radioembolization alone) by the research coordinator using a random assignment generator.

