Trial Population: This trial will consist of up to 104 adults (52 per group) scheduled for radioembolization of a previously untreated HCC mass less than 6 cm in diameter at Thomas Jefferson University.

Trial Procedures: Subjects eligible for trial enrollment will be identified by Jefferson's patient population of subjects being seen for sub-lobar radioembolization of HCC. These patients will be accrued from the Hepatology department, as well as from the HCC Multidisciplinary Tumor Board of the Kimmel Cancer Center at Thomas Jefferson University. A research coordinator will explain the study to the patient. The patient will be given time to consider the risks and benefits of the study and ask questions about participation. The coordinator will review the consent form with the patient and then the patient will be given the form to review. The patient, coordinator, and a study investigator will all sign the consent form. The patient will be given a copy of the signed consent form for their records. A research coordinator will explain the study to the patient. The patient will be given time to consider the risks and benefits of the study and ask questions about participation before providing informed consent. If the subject is a woman of childbearing potential, she will have a urine pregnancy test (the results of which will be made available to her prior to study initiation) prior to each ultrasound exam. Patients will be randomly assigned to either the experimental (UTMD + radioembolization) or control group (radioembolization alone) by the research coordinator using a random assignment generator.

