3.1 Trial Duration

Individual participation for patients within the experimental arm will be limited to 3 ultrasound exams. If patients are unable to make one of the 7, or 14 day visits they will still be eligible to participate. The first CEUS exam will take place 1-6 hours post radioembolization during the patient's clinically scheduled observation period. Exams at approximately 7 and 14 days post treatment will take place during separate visits to Thomas Jefferson University. The entire ultrasound imaging protocol will require approximately 90 mins including a 30 min observation period. For patients assigned to the control arm, no additional participation will be required. Patients who receive ultrasound contrast agent will be monitored for at least 30 minutes before being discharged. The research coordinator will obtain laboratory values, imaging data, and outcomes for comparison to the experimental group (all obtained as part of the patient's clinical standard of care). Subject recruitment is expected to last 83 months (March 2017 – December 2023). Analysis and publication of results are expected to take an additional 3 months (January 2024– March 2024). Volunteer Registry Database forms will be submitted to the National Institute of Health's Office of Regulatory Compliance and Quality at the completion of the research study.

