5.4 Blinding and Unblinding Methods

No blinding will be performed as this is a pilot study and all data analysis will be performed immediately following ultrasound intervention.

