6. TRIAL PROCEDURES

6.1 Patient Enrollment

Subjects eligible for trial enrollment will be identified by Drs. [name], [name], [name], and [name] from their patient population (approximately 52 patients annually being treated by yttrium-90 for hepatocellular carcinoma). These patients will be accrued from the Hepatology department, as well as from the HCC Multidisciplinary Tumor Board of the Kimmel Cancer Center at Thomas Jefferson University. A research coordinator will explain the study to the patient. The patient will be given time to consider the risks and benefits of the study and ask questions about participation. The coordinator will review the consent form with the patient and then the patient will be given the form to review. The patient, coordinator, and a study investigator will all sign the consent form. The patient will be given a copy of the signed consent form for their records. A research coordinator will explain the study to the patient. The patient will be given time to consider the risks and benefits of the study and ask questions about participation before providing informed consent. If the subject is a woman of childbearing potential, she will have a urine pregnancy test (the results of which will be made available to her prior to study initiation) prior to each ultrasound exam. Patients will be randomly assigned to either the experimental (UTMD + radioembolization) or control group (radioembolization alone) by the research coordinator using a random assignment generator. For patients in the experimental group, a brief abdominal ultrasound (without contrast) will also be performed prior to radioembolization to ensure the target lesion is visible on ultrasound.

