7.2 Statistical Analyses

Qualitative findings regarding treatment response will be generated by two radiologists based on mRECIST criteria at 1 and 3-4 months post treatment (using the patient's clinically scheduled contrast-enhanced MRI or CT exams). In the event of conflicting outcome reports, outcomes will be evaluated in consensus.

All statistical analysis will be performed by [name] (SKCC Biostatistics Core and faculty member) using SAS version 9.4 (Cary, NC). Aim 1: The primary hypothesis that UTMD improves the effect of

radioembolization on tumor response in HCC patients will be tested with a non-parametric Mann-Whitney U-test of the difference in response distributions between control (radioembolization alone) and experimental group (UTMD + radioembolization), measured at 3-4 months post treatment. The outcome variable in this analysis, the mRECIST score, is treated as an ordinal variable in this analysis. **Aim 2:** To test if tumor perfusion measured by CEUS between UTMD pulses predicts HCC response to radioembolization, perfusion will be characterized in terms of contrast replenishment time intensity curves fit with a 2-parameter exponential recovery curve as described above. The relationship between the normalized profusion values from this image processing and the patients' subsequent mRECIST scores in the UTMD + radioembolization group will be evaluated with Spearman's rank order correlation.

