APPENDIX A - INVESTIGATOR OBLIGATIONS

A. Institutional Review Board (IRB) and Human Subjects Research Review Board (HSRRB) Review/Approval

The protocol and informed consent for this study must be reviewed and approved by an appropriate IRB and HSRRB prior to enrollment of participants in the study. It is the responsibility of the investigator to assure that all aspects of the ethical review are conducted in accordance with FDA Regulations 21 CFR Part 56. A letter documenting the IRB and HSRRB approval which specifically identifies the study/protocol must be obtained by the investigator prior to initiation of the study. Amendments to the protocol will be subject to the same requirements as the original protocol. The HSRRB must review and approve each modification to the study prior to implementation.

A progress report with a request for re-evaluation and re-approval will be submitted by the investigator to the IRB and HSRRB at intervals required by the IRB, and not less than annually.

After completion or termination of the study, the investigator will submit a final report to the IRB. This report should include: deviations from the protocol, the number and types of participants evaluated, the number of participants who discontinued (with reasons), results of the study, if known, and all AEs, including deaths.

B. Informed Consent

Signed, written informed consent which conforms to FDA Regulation 21 CFR Part 50, must be obtained from each participant prior to entering the study. Each participant will be provided a written consent form and verbal information in an understandable manner which describes the nature and duration of the study. The research study coordinator or the investigator will conduct the informed consent interview in a private examination room. The potential subject will be allowed to discuss the study with the investigator, research study coordinator, or any persons who may have accompanied the potential subject. Additionally, the participant must be allowed adequate time to consider the potential risks and benefits associated with his participation in the study. The research study coordinator will sign the informed consent as the person conducting the consent interview.

C. Data Reporting and Data Forms

Data reflecting participant's experiences with the study will be recorded on CRFs by the investigator.

D. Records Retention

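### The coordinator who conducts consent and collects outcome data also makes each assignment, with no concealment described, and 6.1 places one eligibility check after assignment in the experimental arm only

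*Combined protocol and SAP*

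**What the plan says.** **Assignment.** Section 5.3 is one sentence: patients are allocated "by the research coordinator using a random assignment generator". The synopsis, section 3 and section 6.1 repeat it without adding detail.

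**Other duties of the same role.**
- Consent (6.1): "A research coordinator will explain the study to the patient" and "The coordinator will review the consent form with the patient and then the patient will be given the form to review". Appendix A, part B adds: "The research study coordinator will sign the informed consent as the person conducting the consent interview".
- Data collection (3.1): "The research coordinator will obtain laboratory values, imaging data, and outcomes for comparison to the experimental group".

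**Setting.** Section 3 describes one site and an open-label design. Section 5.4 states: "No blinding will be performed as this is a pilot study". Only the SPECT reads are called blinded (synopsis and 6.5).

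**Scoring of the primary endpoint (7.2).** "Qualitative findings regarding treatment response will be generated by two radiologists based on mRECIST criteria at 1 and 3-4 months post treatment", with consensus if they disagree.

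**Size.** The synopsis gives "up to 104 adults (52 per group"), and 7.2.1 derives 52 per group. Section 1.2 still says 26 per group.

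**Visibility check.** Section 4.1 makes visibility on grayscale ultrasound an inclusion criterion. The synopsis (Trial Procedures) and 6.1 describe the check for the experimental group only, and 6.1 puts it after the assignment sentence. Section 6.2 describes the same check with no limit to one arm.

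**The concern.** In an open-label trial nothing masks allocation afterwards, so concealment before assignment is the main protection against selecting patients into arms. Here the person speaking with the patient at consent also operates the generator. Nothing described prevents that person from knowing or anticipating the next assignment, and no one independent holds a sequence against which assignments could be checked.

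The visibility check raises a related problem. A check confined to the experimental group can be done only once the arm is known. If it fails, a patient can leave the experimental arm for a reason never applied to controls. The arms would then differ in the kind of lesion they contain.

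The harm in both cases is bias in the treatment comparison. The planned Mann-Whitney test is unadjusted. Section 7.2.1 intends to put potential confounders into regression models but names none, and adjustment cannot remove selection on factors that were not recorded.

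**Working it through.** **1. The 52 per group.** Inputs from 7.2.1: effect 0.6, power 85%, type I error 5%. Assumptions: two-sided test, and 0.6 read as a standardised difference.
- Two-sample normal formula: 2 × ((1.960 + 1.036) / 0.6)² = 49.9 per group.
- Divide by the Mann-Whitney asymptotic relative efficiency, 3/π = 0.955: 52.2 per group.
- Power at 52 per group: 84.8%, against 85% stated. The figure reproduces.

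**2. Foreseeable assignments under different schemes.** The plan does not say which scheme applies, so each row is conditional.

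| Scheme | Formula | Forced assignments of 104 |
|---|---|---|
| Simple 1:1, no cap | none forced | 0 |
| One shuffled list of 52 + 52 | 2n/(n+1) = 104/53 | 1.96 |
| Simple 1:1, stopped at n = 52 in either arm | 2n × C(2n,n)/4ⁿ = 104 × 0.0781 | 8.12 |
| Blocks of 8, size known to the assigner | 13 blocks × 8/5 | 20.8 |
| Blocks of 4, size known to the assigner | 26 blocks × 4/3 | 34.7 |

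For the capped simple scheme, the probability of exactly r forced assignments is 2 × C(2n−r−1, n−1) / 2^(2n−r). With n = 52 this gives a median of 7, a 5th-95th percentile range of 1 to 19, and a 35% chance of 10 or more. A simulation of 100,000 sequences gave a mean of 8.14. With the 26 per group of section 1.2, the mean is 5.7.

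**3. Cost of leaving simple assignment uncapped.** Group sizes would then vary, with a 95% range of 42 to 62 in one arm. Power at a 42/62 split is 83.5%, against 84.8% at 52/52. Unequal numbers are not the problem.

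**4. The visibility check, passage against passage.**

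| Place | Which patients | Timing |
|---|---|---|
| 4.1 | all (inclusion criterion) | not stated |
| Synopsis, Trial Procedures | experimental group | before radioembolization |
| 6.1 | experimental group | before radioembolization, listed after assignment |
| 6.2 | no arm limit | before radioembolization |

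Section 4.1 requires visibility of everyone, while the synopsis and 6.1 verify it in one arm. Section 6.2 could be read as covering both arms, but it does not place the check before assignment.

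**The case against.** Several points on the other side stand.

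- **The figure of 8 is not in the plan.** A reader might infer from 52 per group that about 8 late assignments will be foreseeable. That needs both simple randomisation and a hard cap, and neither is stated. The target is worded as an upper limit, and 7.2.1 gives 52 as a sample-size requirement, not an enforcement rule.
- **Silence is not a statement.** A reader might infer that the generator is unstratified and unblocked. The text names no strata, blocks or list, but it does not exclude them. Not stated is as far as it goes.
- **The coordinator does not score the primary endpoint.** A reader might infer control of the outcome as well as of entry. The role retrieves standard-of-care data, and two radiologists score mRECIST. Whether those readers are blinded is a separate matter.
- **Others take part in entry.** Investigators identify candidates from their own patients, who must already be scheduled for radioembolization. An investigator also signs consent, and 6.1 lists consent before assignment. This narrows the room for selection but does not replace concealment.
- **Chance imbalance is generic.** For a hypothetical factor present in half of patients, a difference of at least 10 points between arms of 52 means at least 6 patients. Its exact probability is 28% (31% by normal approximation). The plan gives no effect of tumour size on mRECIST and already limits diameter to below 6 cm. This supports stratification as an option and does not show an error.

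What remains is the combination of duties the plan assigns to one role, the absence of any described concealment, and the one-arm visibility check.

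**Conclusion.** The point holds in limited form. The plan gives consent, assignment and outcome-data collection to one role in a single-site, unblinded trial. It describes no concealment or independent holder of the sequence, and it leaves the type of randomisation and any strata unstated. It also contradicts itself on whether ultrasound visibility is checked in both arms. As 6.1 reads, patients can be screened out of the experimental arm after allocation is known.

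No single number measures the exposure. The worked schemes run from 0 forced assignments to about 35 of 104. The value of about 8 belongs to simple 1:1 assignment capped at 52 per arm and should be quoted only with that condition. The size of any resulting bias cannot be derived from the documents. The change is worth making because the gap concerns the validity of the comparison and is cheap to close.

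**What to change.** **In 5.3:** have the Biostatistics Core, already named in 7.2, generate and hold a 1:1 list in randomly varying permuted blocks, with block sizes not disclosed to the coordinator. Blocking alone is not enough, because small blocks known to the assigner raise predictability (step 2). State the type of randomisation and whether there are strata.

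**Release rule:** issue each assignment only after consent and all eligibility checks are logged, including ultrasound visibility for every patient in both arms. Reconcile the synopsis and 6.1 with 4.1 and 6.2 on who has the visibility check and when.

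**Cost:** one-off list preparation, minor administration per assignment, and the brief non-contrast ultrasound done before assignment for everyone. Section 6.2 already describes that scan without an arm limit.

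**Optional:** stratify by baseline tumour diameter and use the matching stratified (van Elteren) form of the Mann-Whitney test. This would change the primary analysis in 7.2 and need a pre-stated cut-point, so it is a design preference and not part of the correction.

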5.4 Blinding and Unblinding Methods

No blinding will be performed as this is a pilot study and all data analysis will be performed immediately following ultrasound intervention.

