3. TRIAL DESIGN

This is an open-label, randomized trial that will be conducted at one clinical site to determine if ultrasound-triggered microbubble destruction (UTMD) can be used to improve radioembolization of HCC. The subject population will be patients scheduled for radioembolization of a previously untreated HCC mass at Thomas Jefferson University. All patients will undergo single-photon emission computed tomography (SPECT) imaging as part of their standard of care to confirm effective localization of the Y90 beads. For research purposes, imaging of the chest will be performed when possible to assess extrahepatic distribution of Y90 using a planar imaging acquisition. Patients will be randomly assigned to either the experimental (UTMD + radioembolization) or control group (radioembolization alone) by the research coordinator using a random assignment generator. For patients assigned to the experimental group, the study will consist of up to three contrast-enhanced ultrasound (CEUS) exams: 1-6 hours post radioembolization, and approximately 7 and 14 days post treatment. Treatment response will be evaluated using modified response evaluation criteria in solid tumors (mRECIST) at 1 and 4 months post treatment based on the patient's clinically scheduled

contrast-enhanced MRI or CT. For patients assigned to the control group, only outcomes data will be collected (without intervention).

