Study participation for those assigned to the experimental group will consist of up to three contrast-enhanced ultrasound exams. The primary measure of tumor response will be evaluated using mRECIST criteria as determined by Drs. [name] and [name] in consensus using the patients clinically scheduled 3-4 month contrast enhanced MRI or CT. As a secondary measure of tumor response, when available, changes in alpha fetal protein (AFP; collected as blood samples at 1 month as standard of care) will be recorded. Finally, each patient's progression free survival and overall survival will be monitored, although this is a tertiary outcome for this study and many patients are expected to surpass the timeline of this pilot study. Safety outcomes will be determined using changes in vital signs, observed and self-reported adverse events, changes in liver function tests (LFTs) at approximately 1 month post-embolization (preformed as part of clinical standard of care), and distribution of radioactivity on SPECT imaging. Liver function tests (LFTs) include blood tests for alanine aminotransferase, alkaline phosphatase, asparate aminotransferase, bilirubin, albumin, total protein, and prothrombin time.

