6.5 Efficacy Assessments

The primary measure of tumor response will be evaluated using mRECIST criteria as determined by Drs. [name] and [name] in consensus using the patients clinically scheduled 3-4 month contrast enhanced MRI or CT. As a secondary measure of tumor response, changes in alpha fetal protein (AFP; collected as blood samples at 1 month as standard of care) will be recorded. Finally, each patient's progression free survival and overall survival will be monitored, although this is a tertiary outcome for this study and many patients are expected to surpass the timeline of this pilot study. Safety outcomes will be determined using changes in vital signs, observed and self-reported adverse events, and changes in liver function tests (LFTs) at 1 and month post-embolization (preformed as part of clinical standard of care). Liver function tests

(LFTs) include blood tests for alanine aminotransferase, alkaline phosphatase, asparate aminotransferase, bilirubin, albumin, total protein, and prothrombin time. SPECT imaging will be evaluated for all available cases by two blinded radiologists to evaluate if the initial UTMD session skews Therasphere distribution in the liver.

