To answer the secondary hypothesis of whether contrast reperfusion can predict treatment outcomes earlier than conventional MRI/CT imaging at 3-4 months, changes in imaging data from the experimental group will be quantified. The contrast replenishment time intensity curve will be fit with a 2-parameter exponential recovery curve: $VI = \alpha(1 - e^{-\beta t})$, in which VI represents video intensity; α (decibels) represents the asymptotic plateau correlative of the microvessel cross-sectional area, and β (in mm/s) represents the blood velocity. The product $\alpha \times \beta$ is an estimate of perfusion or blood flow per tissue unit (approximately ml/(s mg)) [Krix et al. 2003]. Parametric images from multiple slices in the tumor will also be compiled into a parametric volume to enable visualize of perfusion throughout the mass. Regions of interest will then be selected by Drs. [name] and [name] to determine average perfusion of the mass, peripheral perfusion, and vascular heterogeneity. These values will be quantified for each time point and normalized to D-CEUS at day 1. Normalized values will be grouped based on tumoral response as complete response, partial response, stable disease, and progressive disease (based on mRECIST by 3-4 month contrast-enhanced MRI/CT) to determine if D-CEUS provides an earlier indication of treatment response. Finally, changes in perfusion during the same infusion will be quantified to determine if tumor vascularity is altered during the process of UTMD.

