7.2.1 Sample Size Calculation

Aim 1: Little is known about the effect of UTMD on radioembolization in humans. When comparing similar groups in our animal studies, we observed relative effect sizes of 0.4 and 0.9 for tumor growth and survival, respectively. These animal study results may not apply directly to humans, but they demonstrate that large effect sizes are plausible for this intervention in subjects with HCC tumors. Under these assumptions, we have determined that a sample size of 52 patients randomized to each group would be needed in order for a Mann-Whitney U-test to have 85% power to detect a similarly moderately large relative effect of UTMD on the mRECIST score (i.e., 0.6) with a 5% type I error rate. A similar analysis is planned to compare mRECIST evaluations between 1 month and 3-4 month MRI to determine if earlier cross-sectional imaging can be used to predict long-term treatment response. Relative effect sizes for LFT, AFP, pathology, blinded reads from SPECT, planar imaging, and time to next treatment are expected to be similarly large and will also be evaluated using appropriate non-parametric or exact tests, and are each subject to the same power considerations as for the primary endpoint. Confounding of the results will be investigated and potential confounders will be included in ordinary least squares (OLS) regression models (or quantile regression models, depending on the adequacy of the data meeting OLS modeling assumptions) of these endpoints. Aim 2: A sample size of 52 would provide a two-sided test having 5% type I error rate at least 80% power to detect a Spearman's correlation of 0.4 or greater in the population. Confounding will also be evaluated for this aim and regression analysis will be considered similarly as described for Aim 1.

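### Section 5.4 rules out blinding for a reason that cannot cover the 3-4 month mRECIST read, and nothing masks the readers of the primary endpoint

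*Combined protocol and SAP*

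**What the plan says.** Section 3 discloses the design: "This is an open-label, randomized trial". Section 5.4 then gives the only general statement on blinding: "No blinding will be performed as this is a pilot study and all data analysis will be performed immediately following ultrasound intervention".

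The primary endpoint is the mRECIST category. The synopsis and Sections 3 and 6.5 have two named doctors assess it "in consensus using the patients clinically scheduled 3-4 month contrast enhanced MRI or CT". Section 7.2 describes the read as follows: "Qualitative findings regarding treatment response will be generated by two radiologists based on mRECIST criteria at 1 and 3-4 months post treatment". It adds that conflicting reports go to consensus. None of these places says what the readers know about arm or about contrast-ultrasound (CEUS) perfusion.

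For a different image the plan does mask. The synopsis and Section 6.5 both state: "SPECT imaging will be evaluated for all available cases by two blinded radiologists". Section 7.2.1 lists further endpoints that include "blinded reads from SPECT, planar imaging, and time to next treatment".

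mRECIST is also the reference outcome for Aim 2. Section 6.5 says of the perfusion measurements: "Normalized values will be grouped based on tumoral response as complete response, partial response, stable disease, and progressive disease". Section 7.2 correlates perfusion with the mRECIST score by Spearman's method.

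**The concern.** Section 5.4 gives two reasons for not blinding: pilot status, and analysis straight after the ultrasound. The second may fit the perfusion analysis but cannot fit a read made months later. The first does not explain why SPECT readers can be blinded and mRECIST readers cannot.

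The mRECIST category needs reader judgement. If the readers know the arm, a shared expectation can move borderline scans in one direction, and the Aim 1 Mann-Whitney test would count that shift as a treatment effect. If they know the perfusion results, the Aim 2 correlation may be affected as well. Later analysis cannot remove a bias built into the reads.

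**Working it through.** **1. Timing.** The exams are at 1-6 hours, about day 7 and about day 14 (Section 3). The primary read uses the 3-4 month scan (Sections 3, 6.5 and 7.2). Neither that read nor the Aim 1 test can directly follow an ultrasound session.

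**2. What is masked, and where.**

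| Read | Where described | Masking stated |
|---|---|---|
| mRECIST, 1 and 3-4 months (primary at 3-4 months) | Synopsis; Sections 3, 6.5, 7.2 | None |
| SPECT distribution | Synopsis; Sections 6.5, 7.2.1 | Blinded; to what is not stated |
| Trial as a whole | Section 5.4 | None will be performed |

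**3. The plan's sample size.** This fixes the arm size and sidedness for step 4. Inputs from Section 7.2.1: relative effect 0.6, power 85%, type I error 5% (sidedness not stated for Aim 1). Taking 0.6 as a standardized difference and a two-sided test:

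- n per arm for a comparison of means = 2 × [(1.960 + 1.036)/0.6]² = 49.9.
- Dividing by the Mann-Whitney efficiency 3/π gives 49.9 × π/3 = 52.2 per arm. Power at 52 per arm is 84.8%.

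The planned 52 per arm therefore reproduces. A one-sided test would give 41.8 per arm and does not reproduce it.

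**4. Size of the exposure, on assumptions that are not in the documents.** There is no true effect, and both arms (52 each) have the same true distribution of complete response, partial response, stable disease and progressive disease (CR/PR/SD/PD). A fraction u of experimental-arm reads that are not CR is moved up one category; control reads are untouched. The test is a tie-corrected Mann-Whitney at two-sided 5%. With 200,000 simulated trials per cell, the simulation error is at most about 0.1 percentage point.

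Two-sided type I error (%):

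| Assumed CR/PR/SD/PD (%) | u = 0 | u = 10% | u = 20% | u = 30% |
|---|---|---|---|---|
| 75/15/7/3 | 5.0 | 5.3 | 6.4 | 8.5 |
| 60/25/10/5 | 5.0 | 5.8 | 8.2 | 12.4 |
| 50/30/15/5 | 5.0 | 6.1 | 9.5 | 15.3 |
| 40/30/20/10 | 5.0 | 6.1 | 9.7 | 15.9 |
| 30/40/20/10 | 5.0 | 6.8 | 12.6 | 22.5 |

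Expected number of changed scans = 52 × (1 − CR) × u. At u = 10% this runs from 52 × 0.25 × 0.10 = 1.3 to 52 × 0.70 × 0.10 = 3.6. At 20% it is 2.6 to 7.3, and at 30% it is 3.9 to 10.9. A lower assumed CR share (20/40/30/10) gives 5.0, 7.4, 14.8 and 27.7%.

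**5. Direction.** A smaller simulation (6,000 trials per cell; mixes 70/20/7/3, 50/30/12/8 and 30/40/20/10) counted only false significant results favouring UTMD. These were 2.3-2.6% with no upgrading, 4.1-6.1% at 10%, 6.7-12.4% at 20% and 9.6-22.1% at 30%. Most of the excess error therefore favours the experimental arm.

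**The case against.** Section 5.4 sits under Medications, directly after randomization, in a trial declared open-label. It can be read as covering treatment allocation only. On that reading it does not contradict the blinded SPECT reads; it is simply silent about image readers. That is a fair reading, and it weakens the charge of contradiction. It does not supply the missing masking, and Section 5.4 taken literally excludes it.

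The size is wholly assumed. The model shifts one arm in one direction and supposes that the shift survives a two-reader consensus. The top figure of 22.5% needs about 11 of 52 experimental scans upgraded. This stands: the numbers illustrate the exposure and do not measure it. Consensus, however, reduces random disagreement and does not remove an expectation that both readers share.

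The Aim 2 point depends on the mRECIST readers knowing the perfusion results. Names are removed from the public text, so overlap between the two sets of readers cannot be checked. If perfusion analysis really is completed straight after each exam, it already precedes the response scans. This part is therefore a possibility only.

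Part of the document next to the personnel-roles section of Appendix A was not available for review, so a statement on masking there cannot be excluded.

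**Conclusion.** The concern holds and should be fixed. The timing reason in Section 5.4 cannot apply to the primary read, the unqualified sentence does not sit with the blinded SPECT reads, and no available text masks the mRECIST readers. The case rests on the design: a single, reader-judged primary endpoint in an open-label randomized comparison. Pilot status does not answer it, because the same pilot blinds its SPECT readers and is powered at 85% for a test of its primary hypothesis.

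Under the assumptions above, the inflation is small if a tenth of eligible experimental reads are upgraded, and material at a fifth to a third of them. The documents do not show what the readers will know, so no actual bias is claimed.

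**What to change.** Replace Section 5.4 with wording to this effect:

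> Treatment is open-label for patients and operators. The two radiologists read de-identified 1-month and 3-4-month MRI/CT masked to arm and to all CEUS data, with masked consensus for conflicts. SPECT reads remain blinded. CEUS regions of interest are finalised before mRECIST results are available.

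Use the same wording in the synopsis and in Sections 3, 6.5 and 7.2. This also settles whether consensus is the read itself (synopsis, Sections 3 and 6.5) or only the way to resolve conflicts (Section 7.2). Add what the SPECT readers are masked to. For patients with several treated tumours, say how the target lesion is marked in both arms without revealing treatment.

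**Cost.** The main work is protocol text and de-identification of scans. Section 3.1 already gives the coordinator part of the task: "The research coordinator will obtain laboratory values, imaging data, and outcomes for comparison to the experimental group". That sentence follows text on the control arm, so handling experimental-arm scans may be extra work. No new scans are needed, and the sample size does not change. The same two radiologists can read, unless they also treat the patients and recognise cases. Batch reading reduces that risk but does not remove it, and other readers might then be needed. Masking also assumes that the 3-4 month scans do not usually reveal UTMD, which the documents do not address.
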